### 7.3 Study Medication

All patients are treated with EDS-EP.

## 7.4 Analysis Variables

### 7.4.1 Disposition

Patient disposition data is collected on the 'End of Study' eCRF page when a patient completes or discontinues the study. The date of completion/discontinuation and the reason for discontinuation are recorded. If a patient dies the date of death and if an autopsy was performed is recorded.

For sites in Italy and USA who note the patient as having completed the study this is summarised as "Study Terminated by Sponsor" as the patients participation in the study ended when the study was terminated. This was confirmed by the respective Principal Investigators in writing and confirmations were filed in eTMF.

For sites in India the study was terminated by the sponsor due to the impact of the COVID-19 pandemic. For patients who were discontinued due to such specific COVID-19 related study termination the reason for discontinuation is displayed in summary tables and listings as "Study terminated by sponsor due to COVID-19".

### 7.4.2 Demographic and Other Baseline Characteristics

#### Age

Age (years) is calculated at Baseline based on the date of informed consent as recorded on the 'Informed Consent' eCRF page and the date of birth as collected on the 'Demography' eCRF page as:

$$\text{INT}(\text{date of informed consent} - \text{date of birth})/365.25).$$

Where INT denotes the integer part of the calculation. In case of incomplete dates, missing days are set to 16th and missing months are set to June. If, as a result of this imputation, the age of the patient is 5 years, then the age is set to 6 years.

#### Age categories

Age is classified into the following categories:

- 6 to <10 years,
- ≥ 10 years]

#### Region

Region is derived from the location of the Site and is classified into the following categories:

- India
- Europe, Australia, Tunisia
- United States

#### Sex

As recorded on the 'Demography' eCRF page.

#### Ethnicity

"Hispanic or Latino" or "Not Hispanic or Latino" as recorded on the 'Demography' eCRF page.

#### Race

"White", "Black", "American Indian or Alaska native", "Asian" or "Native Hawaiian or other pacific islander" as recorded on the 'Demography' eCRF page. Multiple answers are possible.

**Height**

As recorded on the 'Vital Signs' eCRF pages. Where triplicate measurements are available the mean of the three values is used for summary statistics at that visit/timepoint.

**Weight**

As recorded on the 'Vital Signs' eCRF page. Where triplicate measurements are available the mean of the three values is used for summary statistics at that visit/timepoint.

**BMI**

As recorded on the 'Vital Signs' eCRF page. Where triplicate measurements are available the mean of the three values is used for summary statistics at that visit/timepoint.

**7.4.3 Medical History**

Past and current medical conditions including Adverse Events resolved in study IEDAT-02-2015 are recorded at screening on the 'Medical History' and 'Medical History Open Label' eCRF pages. For each CRF-requested body system the investigator's assessment of normal/abnormal is recorded, and in case of abnormal the following parameters are recorded: Diagnosis (coded using MedDRA), start date and end date/ongoing.

AT Disease History is recorded at IEDAT-02-2015 study screening visit and verified with proven genetic diagnosis of AT (prior documentation or by central laboratory test report). No additional information is recorded in the OLE-IEDAT study eCRF.

**7.4.4 Concomitant Medication**

Prior and Concomitant medication data are collected throughout the study on the 'Prior / Concomitant Medications' eCRF page. For each Medication (coded using WHO-DD) the start date (or "Not known"), the end date (or "Not known") / Ongoing, Dose, Unit, Frequency, Route and Indication (with corresponding AE number, if applicable) are recorded.

All medications have a start day and end day calculated as described in section 7.2, 'Prior medications' are medications that were stopped before first Study Treatment administration. All other medications are regarded as 'Concomitant medications'.

**7.4.5 Non-drug Therapy and Procedures**

Data on Non-drug Therapy and Procedures are collected throughout the study on the 'Non-drug Therapy and Procedures' eCRF page. For each therapy or procedure (coded using MedDRA) the start date, the end date/ Ongoing, and the reason for use are recorded.

**7.4.6 Measurements of Exposure and Treatment Compliance**

*The EryDex System (EDS) is used to load dexamethasone sodium phosphate (DSP), a marketed drug, into autologous erythrocytes, creating the EDS end product (EDS-EP), which is infused once per month into the patient. The study treatment consists of a dose range of ~14-22 mg dexamethasone sodium phosphate (DSP) administered via ex vivo encapsulation into autologous erythrocytes (EDS) that are infused into the patient.*

Data on EDS-EP infusions are recorded on the 'EDS-EP Infusion' eCRF page. Data on the DSP concentration in µg/mL are provided directly from a third-party vendor. Data on DSP concentration is converted to mg/bag using the following formula:

- $\text{Result (mg/bag)} = \text{Result (}\mu\text{g/mL)} * 78.7 / 1000.$

### Number of infusions received

Number of infusions received is derived as the total number of infusions completed, as determined by response to “Was EDS-EP infusion completed”, during the OLE-IEDAT study. This count includes unscheduled visits.

In addition, as the number of infusions during the ATTeST study varies with the original treatment arm, and the timing of the switch from placebo to active, the total number of infusions from the ATTeST baseline is also calculated.

### Duration of treatment

Duration of treatment on OLE-IEDAT study is derived as:

- Date of Last Infusion – Date of First OLE-IEDAT Infusion + 1.

The overall duration of active treatment from ATTeST baseline is derived as:

- Date of Last Infusion – Date of First Infusion of Active Treatment + 1.

For a definition of Date of first/last OLE-IEDAT infusion and date of first infusion of active treatment, see section 7.1.

### 7.4.7 Efficacy Variables

The “Modified” International Cooperative Ataxia Rating Scale (mICARS) is the most important of the secondary efficacy endpoints.

#### ICARS

*The ICARS is a 100-point, semi-quantitative scale offering a compartmentalized quantification of the following 4 sub-scores: Posture and Gait Disturbances (34 points), Kinetic Functions (52 points), Speech Disorders (8 points), and Oculomotor Disorders (6 points). (Trouillas, et al., 1997)*

*To maximize the consistency of the data obtained from the ICARS, the same site’s neurologist, qualified, trained, and certified in the use of the ICARS and with expertise in the field of AT disorders, will evaluate the same patient at approximately the same time throughout the study. ICARS ratings should be completed without consulting scores from the previous visit.*

*The primary efficacy endpoint is based on the Modified International Cooperative Ataxia Rating Scale (mICARS) score. This modified ICARS excludes items 17-19 related to oculomotor function, and Items 8-12 related to kinetic functions from the full 100-point ICARS.*

The modified ICARS is rescored, collapsing categories within specific items. This method results in a smaller total sum score across the ICARS domains. This is referred to as Rescored mICARS, to prevent confusion with modified ICARS. The rescoring method is outlined in Appendix 2 (Section 13.2) of this SAP. The ICARS is collected on the ICARS eCRF page. For the purpose of analysis, the total scores will be derived. If any of the individual ICARS scores contributing to the total score of interest are missing, then the total score will be set to missing.

The endpoints are the change of the mICARS and RmICARS scores from baseline to Visit 7 (6 Months) and all subsequent measures in 6-month intervals. These endpoints are repeated for all 6-month intervals since start of active treatment as outlined in Section 7.1.

The change in the full ICARS, which is the validated scale and the preference of European Regulators, from baseline to Visit 13 is presented as a sensitivity analysis.

### Modified ICARS score (mICARS)

The ‘Modified’ ICARS (mICARS) score is the total sum of the sub scores excluding Items 17-19 related to oculomotor function and Items 8-12 related to kinetic function; these sub scores

have been removed per FDA request. The ‘Modified’ ICARS score ranges from 0 to 54, with higher scores indicative of more severely affected outcome.

#### **Modified ICARS score - absolute change from OLE-IEDAT baseline**

For any follow-up visit (FU) the absolute change from OLE-IEDAT baseline is calculated as:

- mICARS absolute change from OLE-IEDAT baseline = mICARS score at FU  
- mICARS score at OLE-IEDAT baseline.

#### **Modified ICARS score - absolute change from ATTeST baseline**

For any follow-up visit (FU) the absolute change from the baseline of the ATTeST study is calculated as:

- mICARS absolute change from ATTeST baseline = mICARS score at FU  
- mICARS score at ATTeST baseline.

#### **Rescored Modified ICARS score (RmICARS)**

The Rescored ‘Modified’ ICARS (RmICARS) score is the total sum of the sub scores using the (FDA) scoring approach. The scoring method is presented in Appendix 2 (section 13.2) of this document.

The Rescored ‘Modified’ ICARS score ranges from 0 to 29, with higher scores indicative of more severely affected outcome.

#### **Rescored Modified ICARS score - absolute change from OLE-IEDAT baseline**

For any follow-up visit (FU) the absolute change from OLE-IEDAT baseline is calculated as:

- RmICARS absolute change from OLE-IEDAT baseline = RmICARS score at FU  
- RmICARS score at OLE-IEDAT baseline.

#### **Rescored Modified ICARS score - absolute change from ATTeST baseline**

For any follow-up visit (FU) the absolute change from the baseline of the ATTeST study is calculated as:

- RmICARS absolute change from ATTeST baseline = RmICARS score at FU  
- RmICARS score at ATTeST baseline.

#### **Full ICARS score**

The ICARS score is the total sum of the sub scores and ranges from 0 to 100, with 100 being indicative of the most severely affected outcome.

#### **Full ICARS score - absolute change from OLE-IEDAT baseline**

For any relevant follow-up visit (FU, every 6 months) the change from the baseline of this OLE-IEDAT study is calculated as:

Full ICARS change from OLE-IEDAT baseline = ICARS score at FU - ICARS score at OLE-IEDAT baseline.

#### **Clinical Global Impression CGI-C**

*The CGI (Guy, 1976) is the general name for two scales, the CGI - Change scale (CGI-C) and CGI - Severity scale (CGI-S) (Guy, 1976).*

*The CGI-C scale assesses the change in the patient’s clinical status from baseline using a 7-point scale, ranging from 1 (very much improved) to 7 (very much worse), with a score of 4 indicating no change. In the current study, the change from the patient’s baseline condition will*

*be assessed at all post-baseline visits, will be the key secondary efficacy measure the rater performing the CGI-C will be different from the rater performing the ICARS rating, and will assess the patient without access to the ICARS ratings or safety data.*

*For the CGI-C rating, clinicians will be required to conduct a full clinical interview and examination of the patient, if necessary, with the caregiver present. The interview and examination should assess various aspects of the patient's appearance (grooming, evidence of falls, etc.), ataxia, cognition (orientation, calculation ability, language, ability to follow commands, memory, etc.), apraxia, dysarthria, extrapyramidal motor symptoms, activities of daily living and mood. The CGI-C rating should be based on a holistic assessment of the patient and should not be anchored to specific change or cut-off scores of performance-based measures. It is not necessary for the rater to use specific scales or be guided by their scores for severity; however, the rater may review findings on other measures that are assessed in the trial, e.g. quality of life scale (EQ-5D-5L), to guide their assessments. The raters may also use additional scales or measures to assess specific domains; however, it is important that the raters use the same methods at baseline and at all subsequent visits.*

In the current study, an overall assessment of the change in the patient's neurological symptoms of AT, compared to the status at baseline, are made using the CGI-C. CGI-C scores range from 1 (very much improved) through 7 (very much worse).

The CGI-C score is assessed every 6 months on the 'CGI-C' eCRF page.

#### **Clinical Global Impression CGI-C - categories**

The CGI-C is classified into the following categories:

- Improved (CGI-C score 1-3)
- No change or worsened (CGI-C score 4-7)

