#### *International Cooperative Ataxia Rating Scale (ICARS)*

The ICARS will be used to measure efficacy in the study. The internal consistency, criterion-related validity, and internal construct validity of the ICARS have been established in patients with focal cerebellar lesions (Schoch B et al, 2007). The inter-rater reliability, test-retest reliability and internal consistency have also been validated in patients with spinocerebellar ataxia (Weyer et al, 2007, Schmitz-Hubsch et al, 2006a). The ICARS total score satisfied all psychometric criteria in a validation study in patients with Friedrich's Ataxia (Cano et al, 2005; Metz et al 2013) The ICARS has been used as an outcome measure in interventional studies in patients with ataxia, but there are no clinical data to suggest the magnitude of change on the ICARS that would correspond to a clinically relevant improvement, due to the absence of any drug producing such a benefit. The ICARS has been used in several studies in patients with Friedrich's Ataxia over the age of 8 years, in phase 3 potentially pivotal trials (Lynch et al, 2010), as well as in open-label long-term studies (Meier et al, 2012).

The ICARS was used also in two interventional studies in children with AT. Zanolli et al, 2012 showed a statistically significant decrease in the ICARS total score in a placebo-controlled crossover study in 13 children with AT treated with oral betamethasone (Zanolli et al, 2012). Nissenkorn et al, using ICARS as a secondary endpoint, showed improvement in the static and kinetic subscales in a short-term open-label study in 17 children (from 4 years of age) treated with amantadine (Nissenkorn et al, 2013).

Incoordination of eye movements, nystagmus and loss in saccadic eye movement control is observed early in the AT disease process (Hoche et al, 2012). The ICARS items relating to ocular motility do not provide a comprehensive assessment of this domain. Also, no scale has been validated for the measurement of ocular motility in AT patients. The investigator will be asked to assess the ocular motility item based on the site's clinical paradigm and the instructions for rating the ICARS.

As AT is a severe, relentlessly progressive disorder that leads to loss of independent movement in most patients by the age of 10 to 16 years, any statistically significant difference from placebo over a 6-month period should be considered as a treatment success.

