### 16.2.6 *Efficacy Analyses*

Descriptive statistics (n, mean, standard deviation [SD], median, minimum, and maximum) will be provided for all continuous efficacy measures for actual values and changes from baseline of Study IEDAT-03 at each time-point. For categorical variables, the number and percentage of patients in each category will be presented at each time-point.

The analysis of long-term efficacy of EDS-EP is an exploratory objective of this extension study, and will be based on the results for the "Modified" International Cooperative Ataxia Rating Scale (mICARS), and the Clinical Global Impression of severity and change (CGI-S/C). Descriptive statistics will be performed to determine the proportion of patients who improve, maintain their current state, or worsen after one year of treatment with EDS-EP in this open-label extension study, compared to their baseline status at entry into the IEDAT-03-2018 trial. The mean (SD) change from baseline at each time-point will be evaluated for the mICARS and the CGI-S. For the CGI-Change, the proportion [n(%)] of patients rated as improved, as well as those showing no change or worsening, at each time-point will be calculated.

Additional analyses will be performed to determine the change in each of the efficacy measures compared to the baseline of the IEDAT-02-2015 study, comparing patients who were treated with EDS-EP throughout the double-blind and open-label treatment periods vs. those who received placebo for varying periods in Study IEDAT-02-2015, before being switched to the active treatment. As a secondary objective, similar descriptive analyses will be performed to evaluate the long-term effects of EDS-EP on health-related Quality of Life (QoL), as assessed by the EQ-5D-5L scale.

The details of the statistical analyses will be presented in a separate Statistical Analysis Plan.

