### CGI-S

The individual items of the CGI-S are listed including the CGI-S overall rating (CGI-S structured) for the SAF.

The CGI-S score is analysed as a categorical variable as described in section 8.1. The summary statistics are presented for the FAS and repeated for the subgroups Age (<10 years, ≥10 years) and Region (India; Europe, Australia, Tunisia; United States).

The CGI-S (structured) scores are plotted over time with stacked bar charts for the FAS.

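### The planned CGI-C tables cannot separate stable from worsening patients, and the SAP omits, without declaring it, the protocol's one-year improve/maintain/worsen analysis and the CGI-S mean change

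*SAP*

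**What the plan says.** The SAP (7.4.7, Clinical Global Impression CGI-C) describes a scale from 1, very much improved, to 7, very much worse, "with a score of 4 indicating no change". The categories subsection then defines two groups: "Improved (CGI-C score 1-3" and "No change or worsened (CGI-C score 4-7". SAP 10.6.1 tabulates these proportions on the FAS and repeats them for two age groups and three regions (Tables 14.2-4.1 to 14.2-4.6). It also lists every CGI-C result and plots the scores as stacked bars (Listing 16.2.6-2.1, Figure 14.2-3.2.1).

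Protocol 16.2.6 contains three relevant commitments:

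- Against status at entry to this extension, it promises the "proportion of patients who improve, maintain their current state, or worsen after one year of treatment with EDS-EP".
- "The mean (SD) change from baseline at each time-point will be evaluated for the mICARS and the CGI-S".
- For CGI-C, it asks for the proportion of "patients rated as improved, as well as those showing no change or worsening, at each time-point will be calculated".

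On CGI-S, SAP 10.6.1 says: "The CGI-S score is analysed as a categorical variable as described in section 8.1". Section 8.1 gives frequencies for categorical variables.

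**The concern.** The efficacy question in both documents is whether benefit seen in the preceding trial persists. The protocol's rationale for ICARS says: "As AT is a severe, relentlessly progressive disorder that leads to loss of independent movement in most patients". It also says that no available treatment slows or stops the disease. In that setting, whether patients hold their level or decline is of direct interest, and protocol 16.2.6 asks for it by name. CGI-C is the natural place to answer, because its midpoint already means no change and no cut-off has to be invented. The SAP itself calls CGI-C the key secondary efficacy measure, and SAP section 9 says analyses from this study will support a Briefing Book and an NDA.

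If the tables merge score 4 with scores 5-7, and no other table gives within-patient improve/maintain/worsen counts, the prespecified numerical results leave that question open. An omission that SAP 3.6 does not record also leaves a reader of the study report unable to tell a deliberate change from an oversight.

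**Working it through.** The plan states no figure to reproduce: the study is descriptive, with no formal sample size calculation and no hypothesis tests. The check is a comparison of texts plus one piece of arithmetic.

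**Step 1. What the two-category table carries.** At a given visit let N patients have a CGI-C result, with I improved (1-3), S stable (4) and W worse (5-7), so N = I + S + W. The table reports I/N and (S + W)/N = 1 - I/N. The second row is the complement of the first and adds nothing. S/N can lie anywhere from 0 to 1 - I/N.

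**Step 2. Numbers in.** N = 150 is the protocol's expected maximum enrolment. The improved shares are assumptions, shown as a range.

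| Assumed improved | I | Merged row, 150 - I | Stable share compatible with the table |
|---|---|---|---|
| 20% | 30 | 120 (80%) | 0 to 80% |
| 40% | 60 | 90 (60%) | 0 to 60% |
| 60% | 90 | 60 (40%) | 0 to 40% |

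Two opposite outcomes show the effect at 20% improved. Improved/stable/worse of 20/70/10% is 30/105/15 patients; 20/10/70% is 30/15/105. Both print as 30 (20%) and 120 (80%), although worsening differs by 105 - 15 = 90 patients, or 60 percentage points. Rows for 1-3, 4 and 5-7 would show the difference exactly.

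**Step 3. Protocol commitments against SAP outputs.**

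| Protocol 16.2.6 | SAP 10.6.1 and table list |
|---|---|
| One-year improve/maintain/worsen proportions | None for any scale. mICARS, RmICARS and ICARS have continuous summaries; CGI-S has level frequencies; CGI-C has two categories |
| CGI-S mean (SD) change from baseline | None. Category counts only |
| CGI-C proportions | Two categories, overall and in five subgroup tables |

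**Step 4. Was the change declared?** SAP 3.6 records the wider safety set, a renamed schedule column, the ATTeST treatment groups and the age and region subgroups, the rescored mICARS, continuous exposure and 12-month adverse event periods. It mentions neither the three-way analysis nor the CGI-S mean change.

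**Step 5. Do other outputs fill the gap?** The listing and the CGI-C chart keep score 4 visible, but the figure list has one CGI-C chart and no age or region versions. A mean mICARS change near zero fits general stability or equal numbers improving and declining. CGI-S frequencies by visit are not within-patient change, and their denominators move as patients leave. None gives the promised proportions.

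**The case against.** The strongest reply is that the SAP follows the protocol's own CGI-C sentence. That wording, repeated in the synopsis, can be read as improved versus all others, and the SAP copies it. A reader might infer that the two-way split is itself an undeclared departure; the documents do not support that. The improve/maintain/worsen sentence names no scale, sets no cut-offs and is absent from the synopsis. This part stands. It does not dispose of the separate three-way commitment, which has no counterpart in the SAP whichever way the CGI-C sentence is read.

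A reader might also infer that stability cannot be told from deterioration anywhere in the results. That goes too far. The full score is collected, listed per patient and plotted, and the ICARS summaries and CGI-S frequencies show worsening at group level. The loss is confined to the tabulated proportions.

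A third tempting inference is that a large stable group would demonstrate benefit. The protocol ties treatment success on ICARS to a difference from placebo, and this study has no concurrent control. Its validation data show severity rising with age under 10 years but not above, so no change in older patients may be natural history. A separate row would describe the patients, not prove an effect.

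Finally, the table shells are not in the documents, so two-row tables are inferred from the category definition, and the percentages above are invented for illustration. Both points are fair. The arithmetic shows only that merging discards the information.

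**Conclusion.** The point holds in a limited form. As the SAP defines them, the CGI-C tables cannot separate stable from deteriorating patients; the listing and the single chart can. The clear departures from the protocol are two undeclared omissions: the one-year improve/maintain/worsen proportions and the mean (SD) change for CGI-S.

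The size is known only as a bound. The stable share is undetermined between zero and one minus the improved share, for example 0 to 80% when 20% improve. No document gives an expected distribution.

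This rests on three assumptions: that the CGI-C tables use the SAP's two categories; that the chart plots the individual scores, as its description suggests; and that CGI-C is rated against the extension baseline, which the CGI-C sections do not spell out. The matter concerns descriptive efficacy and leaves the primary safety objective untouched. It should be corrected because the correction is cheap and the protocol asks for the result.

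**What to change.** 1. In SAP 7.4.7 define three CGI-C categories: improved (1-3), no change (4) and worsened (5-7). Report n (%) of each at every 6-month visit, overall and in the age and region repeats. State that the rating is against the OLE-IEDAT baseline, and identify Month 12 as the protocol's one-year improve/maintain/worsen analysis.
2. In SAP 10.6.1 add mean (SD) change from OLE-IEDAT baseline for CGI-S beside the category counts, or declare and justify its removal in SAP 3.6.
3. For mICARS the protocol gives no cut-off for maintaining status and says no data establish a clinically relevant ICARS change. Either define a cut-off, or declare in SAP 3.6 that the three-way analysis rests on CGI-C.

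The cost is one extra row in the CGI-C tables, a few extra CGI-S summary rows and short SAP text. The seven-point score is already collected, so no new data are needed. Exact confidence intervals and a CGI-S baseline-to-visit shift table are optional. The protocol does not promise either, and they would add more output than this, given the ATTeST group columns and subgroup repeats.
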